11.6. Body Weight

Body weight should be measured with no shoes on and using a calibrated scale throughout the study.

11.7. Physical Examinations

Complete physical examinations will include but are not limited to an assessment of general appearance, skin, HEENT (head, eyes, ears, nose, throat), musculoskeletal, thyroid/endocrine, cardiovascular, chest/lung, neurologic, abdomen, and extremities/general body systems, including standard Child-Pugh scoring assessments to determine whether ascites or hepatic encephalopathy are present. Abbreviated physical examinations will include HEENT, cardiovascular, chest/lung, abdomen, and extremities.

11.8. Standard 12-Lead Electrocardiograms

12-lead ECGs are to be performed with subjects in a supine position after at least 5 minutes of rest. For the single dose segments, the standard 12-lead ECG is to be performed during Screening; predose and at 3 hours postdose on Day 1; 48 hours postdose on Day 3; and Early Study Termination, if applicable. For the multiple dose segments, the standard 12-lead ECG is to be performed at Screening; predose and at 3 hours postdose on Day 1; predose on Day 3; 24 hours after the last dose on Day 8; and Early Study Termination, if applicable. The time margin for 12-lead ECGs is 20 minutes for 3 hours postdose.

11.9. Laboratory Evaluations of Safety

Samples for the following laboratory tests will be collected after an overnight fast (at least 8 hours):

- Chemistry: sodium, albumin, ALP, bicarbonate, calcium, bile acids, corrected calcium, chloride, total and direct bilirubin, AST, ALT, BUN, urea, creatinine, magnesium, phosphorus, potassium, creatine phosphokinase (CPK), total cholesterol, triglycerides, high-density lipoprotein cholesterol (HDL-c), low-density lipoprotein cholesterol (LDL-c), lactate dehydrogenase (LDH), gamma-glutamyltransferase (GGT), and total protein
- Hematology: hemoglobin, hematocrit, white blood cell (WBC) count (total and differential), red blood cell count, platelet count, and platelet volume
- Urinalysis (dipstick) (SAD-HS, SD-CP, MAD-HS, and MAD-CP only): leukocyte esterase, nitrites, pH, protein, specific gravity, glucose, occult blood, ketones, bilirubin, urobilinogen, and albumin; microscopic analysis is to be performed only if protein, leukocyte esterase, blood or nitrite is positive
- Coagulation: activated partial thromboplastin time (aPTT), INR, and prothrombin time (PT)
- Pregnancy testing: urine testing on Day -1 for all female SAD-HS, SD-CP, MAD-HS, and MAD-CP subjects and serum testing for all female subjects for all other instances

The urine pregnancy test for female subjects will be conducted locally; all other planned laboratory evaluations of safety will be conducted at a central laboratory. See the laboratory manual for additional details.

11.10. Other Laboratory Evaluations

Samples for the following laboratory tests will be collected after an overnight fast (at least 8 hours):

- Serology: HIV, HBV, HCV
- Non-childbearing confirmation: FSH (females only)
- Drug screen (SAD-HS, SD-CP, MAD-HS, and MAD-CP only): Cannabinoids, cocaine, opiates, amphetamines, barbiturates, and benzodiazepines
- Cotinine screen (SAD-HS, SD-CP, MAD-HS, and MAD-CP only)
- Alcohol screen

The drug and cotinine screens on Day -1 and the alcohol screen at Screening and Day -1 will be conducted locally; all other planned laboratory evaluations will be conducted at a central laboratory. See the laboratory manual for additional details.

11.11. Subject Safety Guidelines

11.11.1. Potential Side Effects

Results from nonclinical studies of EP547 demonstrate a nonclinical profile suitable for advancement into human clinical studies. Refer to the Investigator's Brochure for additional EP547 information regarding nonclinical study results.

11.11.2. Overdose

No specific information is available on the treatment of overdose of EP547. Additionally, there is no specific antidote to EP547. In a case of overdose, appropriate supportive measures should be employed.

12. PHARMACOKINETICS ASSESSMENT

Blood, urine, and skin samples for PK will be utilized to analyze EP547 concentrations; the metabolite profile may also be analyzed from these samples.

12.1. Blood Sampling for Pharmacokinetics

Blood sampling for PK of EP547 will be collected as follows:

- **SAD-HS, SD-CP, and SD-UP:** predose and at 0.25, 0.5, 1, 1.5, 2, 2.5, 3, 4, 6, 9, and 12 hours postdose on Day 1; 18, 24, and 36 hours postdose on Day 2; 48 hours postdose on Day 3; and at follow-up on Day 8.
- **MAD-HS:** predose and at 0.25, 0.5, 1, 1.5, 2, 2.5, 3, 4, 6, 9, 12, and 18 hours postdose relative to the dose of study drug on Day 1; predose on Day 2 through Day 6; predose and at 0.25, 0.5, 1, 1.5, 2, 2.5, 3, 4, 6, 9, 12, and 24 hours postdose relative to the last dose of study drug on Day 7; and at follow-up on Day 14 and Day 21.
- **MAD-CP:** predose and at 0.25, 0.5, 1, 1.5, 2, 2.5, 3, 4, 6, 9, 12, and 18 hours postdose relative to the dose of study drug on Day 1; predose on Day 2; predose on Day 4; predose and at 0.25, 0.5, 1, 1.5, 2, 2.5, 3, 4, 6, 9, 12, and 24 hours postdose relative to the last dose of study drug on Day 7; and at follow-up on Day 14 and Day 21.
- **MAD-UP:** predose and at 0.25, 0.5, 1, 1.5, 2, 2.5, 3, 4, 6, 9, 12, and 18 hours postdose relative to the dose of study drug on Days 1, 2, and 6; predose on Day 4; predose and at 0.25, 0.5, 1, 1.5, 2, 2.5, 3, 4, 6, 9, 12, and 24 hours postdose relative to the last dose of study drug on Day 7; and at follow-up on Day 14 and Day 21.

The MAD dosing and PK blood sampling schedule is summarized in [Appendix C](#). The assessment window for blood sample collection timepoints for the single and multiple dose segments is also included in [Appendix C](#).

12.2. Urine Collection for Pharmacokinetics (SAD-HS Only)

Urine sampling for PK of EP547 will be collected at predose (-6 to 0 hours) and from >0 to 6, >6 to 12, and >12 to 18 hours postdose on Day 1; >18 to 24, >24 to 30, and >30 to 36 hours postdose on Day 2; and >36 to 42 and >42 to 48 hours postdose on Day 3.

12.3. Skin Biopsy for Pharmacokinetics (Last Dose Level for MAD-HS and All Dose Levels for MAD-CP and MAD-UP Only)

Given that EP547 is hypothesized to be an inverse agonist (inhibitor) of MRGPRX4 in the skin to reduce itch, three 3-mm biopsies of the skin from the back will be performed under local anesthesia on Day 1 at 2 hours postdose with an assessment window of +30 minutes. One biopsy will be used for PK to evaluate drug concentrations at the site of action and the other 2 biopsies will be used for PD assessment as described in Section 14.5 to further elucidate the mechanism of action of EP547.

13. CARDIODYNAMIC ASSESSMENT

13.1. Holter Monitoring for 12-Lead ECG Acquisition and Subsequent Cardiodynamic Analysis (SAD-HS Only)

Clinical evaluation of QT/QTc interval prolongation risk and proarrhythmic potential will be conducted for EP547, which is recommended by the US FDA for all new non-antiarrhythmic drugs having systemic bioavailability ([FDA 2005a](#)). Continuous digital 12-lead ECGs will be recorded from approximately 1 hour predose on Day 1 to 24 hours postdose on Day 2 under constant supervision for subjects in SAD-HS only. Subjects will rest quietly in the supine position for at least 10 minutes before each extraction timepoint and for 5 minutes during each extraction with the understanding that a full undisturbed supine period may not be possible given other assessments at competing timepoints. Twelve-lead ECG extraction timepoints will be at -30, -20, and -10 minutes predose on Day 1; at 0.25, 0.5, 1, 1.5, 2, 2.5, 3, 4, 6, 9, and 12 hours postdose on Day 1; and at 18 and 24 hours postdose on Day 2. Twelve-lead ECGs will be extracted from the continuous recording from a 5-minute window preceding the ECG timepoints and scheduled to end 1 to 2 minutes before the scheduled PK draw to conduct early QT assessment based on concentration-QT analysis. Subjects are to continue fasting through 4 hours postdose as food can impact the results.

[REDACTED]

[REDACTED]

[REDACTED]

[REDACTED]

[REDACTED]

[REDACTED]

[REDACTED]

[REDACTED]

[REDACTED]

[REDACTED]

[REDACTED]

[REDACTED]

[REDACTED]

[REDACTED]

[REDACTED]

[REDACTED]

[REDACTED]

[REDACTED]

[REDACTED]

[REDACTED]

[REDACTED]

[REDACTED]

[REDACTED]

[REDACTED]

[REDACTED]

[REDACTED]

[REDACTED]

14.10. Height

Height will be measured using a stadiometer with no shoes.

15. STATISTICS

A formal Statistical Analysis Plan (SAP) will be prepared and finalized before database lock. Additional statistical analysis details will be included in the SAP.

15.1. Populations for Analysis

The following analysis populations will be considered:

- **Enrolled Population:** This population will comprise all subjects who sign the ICF to participate in the study, complete the screening visit procedures, and meet all eligibility criteria for enrollment.
- **Safety Population:** This population will comprise all subjects who receive at least 1 dose of study drug.
- **PK Population:** This population will comprise all subjects who receive at least 1 dose of EP547 and provide adequate blood samples for bioanalysis.
- **PD Population:** This population will comprise all subjects belonging to the Safety Population without major protocol deviations.

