### 3.5 Handling of Missing Data

For the classification of Treatment emergent adverse event (TEAE) and Concomitant medication, the following will be applied in the following order:

- a. If all dates/times (start and stop) missing, the event/medication will automatically be classified as a TEAE/Concomitant medication.
- b. For adverse events (AEs) with a missing start date/time, if the event end date/time is prior to first study drug administration, the event will not be classified as a TEAE.
- c. If only the AE start year/ medication end year is present and is the same or is after the first study drug administration year unit, the event/medication will be classified as a TEAE/Concomitant medication.
- d. If the AE start month and year/medication end month and year are present and are the same or after the first study drug administration month and year units, the event/medication will be classified as a TEAE/Concomitant medication.

For the PK analysis the following will be applied:

- a. For the concentration descriptive summaries, concentrations may be excluded if sampling time deviation is considered large to affect the profile at the discretion of the pharmacokineticist.
- b. Concentrations (plasma and skin) that are below limit of quantification (BLQ which is 10 ng/mL undiluted) prior to the first quantifiable value will be set equal to zero. Post dose BLQ concentrations will be set to missing.
- c. Where there are no results (NR), these will be set to missing.
- d. If more than 75% of values per nominal timepoint and treatment group are BLQ, then all descriptive statistics, except for nBLQ, will be denoted as not calculable (NC).
- e. For the calculation and graphical representation (semi-log and log-log plots) of geometric descriptive statistics, 0 values will be set to missing.
- f. For the purpose of calculating the non-compartmental PK parameters, plasma concentrations that are BLQ prior to the first quantifiable value will be set equal to zero. BLQ values after measurable concentrations will be set to missing.
- g. For the calculation of summary statistics of PK parameters, all NR and NC values in a data series will be set to missing.

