#### 4.1.3 Pharmacokinetic (PK) Population

##### **Plasma PK population:**

Non FE segments: This population will comprise all subjects who receive at least one dose of study drug (EP547) and have any measurable plasma concentrations of EP547 and had no important protocol deviations affecting the pharmacokinetics of EP547 and for whom a sufficient number of samples are available to determine at least one PK parameter among  $C_{max}$ ,  $T_{max}$  and  $AUC_{0-t}$ . Subjects will be assessed on a subject-by-subject basis for inclusion in the PK Population and will be determined by the study and sponsor pharmacokineticist. The PK Population determination will be made before unblinding post database lock.

The PK analyses for EP547 and its metabolites (as applicable) will be conducted based on the PK Population for plasma concentration data.

For FE segment: This population will include all randomized subjects who receive at least one dose of study drug (EP547 75 mg Fasted or EP547 75 mg Fed) who had no important protocol deviations affecting the PK variables of EP547 and for whom a sufficient number of samples are available to determine at least 1 PK parameter among  $AUC_{0-t}$ ,  $C_{max}$  or  $T_{max}$ . All PK analysis will be based on this population. Subjects will be assessed on a subject-by-subject basis for inclusion in the PK Population and will be determined by the study and sponsor pharmacokineticist.

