$t_{1/2}$	
Apparent terminal half-life, using the following formula
 $T_{1/2} = \frac{\ln(2)}{\lambda_z}$
CL/F	
Apparent total plasma clearance, using the following formula
 $CL/F = \frac{D}{AUC_{0-\infty}}$ 
Where D = Administered dose; <math>AUC_{0-\infty} = AUC_{0-inf}</math>

$V_z/F$	
Apparent terminal volume of distribution, using the following formula
 $V_z/F = \frac{CL/F}{\lambda_z} \text{ Or } \frac{Dose}{\lambda_z \times AUC_{inf}}$
Corrected M/P ratio for $C_{max}$	
Corrected metabolite to parent ratio for <math>C_{max}</math> is calculated using the following formulae
 
(<math>C_{max}</math> metabolite/<math>C_{max}</math> parent) *(Molecular Weight of parent drug/Molecular Weight of metabolite)

Corrected M/P ratio for AUC 0-t	
Corrected metabolite to parent ratio for AUC0-t is calculated using the following formulae
 
(AUC0-t metabolite/ AUC0-t parent) *(Molecular Weight of parent drug/Molecular Weight of metabolite)

**Plasma Pharmacokinetic Parameters at steady state on pre-defined days following multiple dose administration for the MAD-HS and MAD-CP segments (Day 1 and Day 7) and for the MAD-UP segment (Day 1, Day 2, Day 6, and Day 7)**

Parameter	Definition
C max	Maximum steady state concentration time over the dosing interval
C trough	The pre-dose trough concentration observed at the last planned timepoint prior to next dosing
T max	Time to reach maximum concentration over the dosing interval. If the same C max concentration occurs at different time points, T max is assigned to the first occurrence of C max .
AUC 0-t	Area under the drug concentration-time curve, from time zero to the last measurable concentration using the 'Linear Up and Log Down' method
AUC 0-τ	Area under the plasma concentration-time curve over a dosing interval using the 'Linear Up and Log Down' method
AUC 0-24hr	Area under the drug concentration-time curve, from time zero (time of dosing) to 24 hours post-dose using the 'linear Up and Log Down' method
AUC 0-48hr	Area under the drug concentration-time curve, from time zero (time of dosing) to 48 hours post-dose using the 'linear Up and Log Down' method

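### SAP 4.1.3 adds an undeclared subject-level exclusion to the plasma PK population, so a PK-affecting deviation on one day or in one period also removes that subject's unaffected profiles

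*Protocol*

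**What the plan says.** Protocol 15.1 sets two conditions for the PK population: "This population will comprise all subjects who receive at least 1 dose of EP547 and provide adequate blood samples for bioanalysis".

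SAP 4.1.3 sets more. For the segments other than food effect, a subject must also "have any measurable plasma concentrations of EP547", must have "had no important protocol deviations affecting the pharmacokinetics of EP547", and must be one "for whom a sufficient number of samples are available to determine at least one PK parameter" among Cmax, Tmax and AUC0-t. The food-effect definition drops the measurability condition and keeps the other two. The unit of decision is the person: "Subjects will be assessed on a subject-by-subject basis for inclusion in the PK Population". The study and sponsor pharmacokineticists make that decision.

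Three other rules can remove plasma data:
- SAP 3.5 works on single samples, and for concentration summaries only: "concentrations may be excluded if sampling time deviation is considered large to affect the profile".
- SAP 10.1 drops the whole subject if the pre-dose value at the first dose exceeds 5% of Cmax.
- SAP 10.1.1.2 sets regression-based parameters to not calculable when the terminal fit or the extrapolated area fails its limit.

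SAP 10.1 derives parameters on Days 1 and 7 in MAD-HS and MAD-CP, on Days 1, 2, 6 and 7 in MAD-UP, and in both periods of FE-HS. SAP 15 states that there are no changes to the planned analysis.

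**The concern.** The SAP criterion is narrower than the protocol's, and the change is not declared. It also acts on the wrong unit for subjects with several profiles. An event late in the dosing week cannot affect a profile already collected. Yet once a later deviation is judged important and PK-affecting, the subject leaves the population and every one of that subject's profiles goes too.

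At stake are the Day 1 summaries in the MAD segments, the Day 1 dose-proportionality slope in MAD-HS, the Day 1 (dialysis) and Day 2 (no dialysis) profiles in MAD-UP, and the unaffected regimen's data in FE-HS. Under SAP 19, concentrations are listed for the Enrolled Population but derived plasma parameters only for the PK population, so an excluded subject's valid parameters would not be listed either.

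**Working it through.** The documents give no sample-size, power or variance figure to reproduce. The check is a profile count plus the effect on the confidence intervals that the SAP plans.

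**Inputs.** Six EP547 subjects per healthy-subject dose level (Protocol 7.1.1). MAD-HS doses of 25, 75 and 225 mg (Addendum, Background and Rationale). Twelve FE-HS subjects (Addendum 7.1). 90% CIs for the slope and the fed:fasted ratio (SAP 3.3). CVs and lost dose fractions are assumptions.

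**1. Profiles kept after one disqualifying deviation**

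| Segment | Profiles | Subject-level rule | Profile-level rule |
|---|---|---|---|
| MAD-HS, one level | 6 × 2 = 12 | 10 | 11 |
| MAD-UP, one level (6 on EP547), Days 6 and 7 affected | 6 × 4 = 24 | 20 | 22 |
| FE-HS | 12 × 2 = 24 | 22 | 23 |

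In MAD-UP, two of the four discarded profiles (Days 1 and 2) were unaffected.

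**2. MAD-HS slope.** The 90% half-width is t(0.95, N−2) × σ / √Sxx. With ln-dose steps of ln 3 = 1.0986 and 6 per level, Sxx = 12 × 1.0986² = 14.483 and t(0.95, 16) = 1.746. With one subject removed, t(0.95, 15) = 1.753.
- Middle dose: Sxx is unchanged, so the ratio is 1.753/1.746 = 1.004, or 0.4% wider.
- End dose: Sxx = 14.483 − 1.0986² × 18/17 = 13.205. The ratio is 1.004 × √(14.483/13.205) = 1.052, or 5.2% wider.

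At an assumed 30% CV, σ = √ln(1.09) = 0.294 and the half-width goes from 0.135 to at most 0.142. SAP 3.3 fits Days 1 and 7 separately, so the Day 1 part of this loss is avoidable.

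**3. Food-effect ratio.** The log-scale half-width is t(0.95, n−2) × s_w × √(2/n).
- n = 12: 1.812 × 0.408 = 0.740 s_w.
- n = 11: 1.833 × 0.426 = 0.782 s_w.
- Ratio: 1.056, or 5.6% wider.

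At an assumed 20% intra-subject CV (s_w = 0.198), the CI factor goes from exp(0.740 × 0.198) = 1.158 to exp(0.782 × 0.198) = 1.167. At 40% it goes from 1.330 to 1.351. Most of this loss remains under profile-level exclusion, because a subject with one period gives no within-subject contrast. What comes back is the unaffected regimen's summary and some between-subject information.

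**4. A retained profile with lost dose.** If one of n subjects keeps a fraction f of true exposure, the geometric mean is multiplied by f^(1/n).

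| Assumed loss | n = 6 | n = 12 (one fed profile) |
|---|---|---|
| 25% | 0.953 | 0.976 |
| 50% | 0.891 | 0.944 |
| 75% | 0.794 | 0.891 |

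At 50% loss, a six-subject geometric mean falls 11% (range 5–21%) and the fed:fasted ratio shifts 5.6% (2.4–11%). The second 5.6% matches the one in step 3 only by coincidence.

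**The case against.** Protocol 15 leaves further analysis detail to the SAP, and only deviations that are both important and PK-affecting count. Pharmacokineticists judge each case, and subjects can be replaced: Protocol 7.2 says non-evaluable subjects will be, Protocol 7.3.2 and 8.4 and Addendum 7.3 say they may be. This reduces the size of the problem but does not remove it. The judgement is written as in or out for the subject. For the non-food-effect segments, SAP 4.1.3 also places it after database lock, when replacement is no longer possible.

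A reader might infer more than the documents support:
- *That deviations are the only trigger.* They are not. The population also requires enough samples and, outside FE-HS, a measurable concentration. SAP 10.1 has the pre-dose rule.
- *That every segment is affected.* SAD-HS, SD-CP and SD-UP give one profile per subject, so no other day can be lost. A missed home dose cannot be the cause in MAD-HS, where confinement is mandatory throughout.
- *That the interval for a dose-level mean widens by 16% when six subjects become five.* The arithmetic is right (0.953/0.823 = 1.159), but SAP 3.1 plans no CI for PK means.
- *That a vomited dose is an AE, not a deviation, and so certainly stays in.* Protocol 11.1.4.1 mentions vomiting only as an AE-recording example, and Protocol 17.1 gives only examples of important deviations. SAP 6 refers the categories to a deviation plan that is not supplied. SAP 3.3 also allows unspecified data adjustments in the food-effect model. The gap was not created by the SAP, since Protocol 15.1 has no emesis rule either.

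**Conclusion.** The point holds in limited form. SAP 4.1.3 narrows the protocol's plasma PK population by an undeclared criterion that acts on the subject. In MAD-HS, MAD-CP, MAD-UP and FE-HS, as written, it discards valid profiles along with the affected one. The cost per lost subject is modest: 0.4% to 5.2% on the MAD-HS slope CI, about 5.6% on the food-effect log-scale CI (largely unrecoverable), and up to two unaffected profiles of four in MAD-UP. These figures assume a full complement, one subject lost, no replacement and an unchanged residual SD.

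The silence on lost doses is a gap in both documents, not a demonstrated bias. Its size rests on an assumed lost fraction. A 50% loss in one top-dose MAD-HS subject would move the slope by 1.0986 × ln(0.5)/14.483 = −0.053, under half the 0.135 half-width at 30% CV. SAP 3.3 does not judge proportionality strictly by statistical rule. No reversed conclusion is claimed. The case for change is that a better rule is available at little cost.

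**What to change.** Keep the Protocol 15.1 population in SAP 4.1.3 and move the deviation criterion to profile level. Drop from summaries and models only the day(s) or period whose dose or sampling was affected, and keep the subject's other profiles. Fix the criteria before database lock, flag excluded profiles in the concentration and parameter listings, and record the change in SAP 15. Let the same evaluability flag cover documented dose loss such as emesis, with its criterion fixed at the same time.

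The cost is SAP wording and one flag in the PK dataset. The drawback is that n can differ between days or periods within a table, so each column needs its own n.

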15.2. Outcome Measures

15.2.1. Primary Safety Outcome Measures

Primary safety outcome measures include:

- AEs
- Clinical laboratory assessments
- Vital signs and body weight
- Standard 12-lead ECGs
- Physical examinations

15.2.2. Secondary Pharmacokinetic and Cardiodynamic Outcome Measures

Secondary PK and cardiodynamic outcome measures include:

- Plasma EP547 and metabolites (as applicable) concentrations
- Plasma PK parameters estimated using noncompartmental analysis (NCA), as appropriate²:
 - SAD segments: C_{max} , t_{max} , k_{el} , $t_{1/2}$, AUC_{∞} , AUC_t , $\%AUC_{extra}$, CL/F , and V_z/F
 - MAD segments: C_{max} , C_{trough} , t_{max} , k_{el} , $t_{1/2}$, AUC_{τ} (as appropriate), AUC_t , CL/F , V_z/F , and R_{ss}

² The PK parameters definitions are in Section 4.

- Urine PK parameters estimated using NCA, as appropriate:
 - SAD-HS segment: A_e , F_e , CL_r
- Skin EP547 and metabolites (as applicable) concentrations
- Holter monitoring for 12-lead ECG acquisition and subsequent cardiodynamic analysis

[REDACTED]

[REDACTED]

[REDACTED]

[REDACTED]

[REDACTED]

[REDACTED]

[REDACTED]

[REDACTED]

[REDACTED]

[REDACTED]

[REDACTED]

